
RATIONALE

The rationale for the proposed trial is summarized below:

1. **More than two-third** of SCD children followed up at Sainte-Justine UHC are either vitamin D deficient or insufficient during summer and fall and may therefore clinically benefit from improving their vitamin D status.
2. Given the low dietary and supplemental intakes of vitamin D of SCD children, their poor compliance to vitamin D supplementation, their compromised cutaneous synthesis of vitamin D, the presence of other potential contributing factors (e.g. impaired vitamin D metabolism, increased

nutritional demands, lactose intolerance) and the poor adherence to the CanHaem clinical practice guidelines¹⁴ regarding vitamin D, a vitamin D nutritional intervention is clinically and ethically desirable.

3. The fact that conditions associated with vitamin D deficiency/insufficiency are similar to SCD-related complications suggests that correcting vitamin D nutrition of these children may potentially result in clinical improvements and ultimately a better quality of life.

4. Very few SCD children in our cohort had serum 25OHD levels > 75 nmol/L (i.e. 6%), the suggested target level for the extra-skeletal effects of vitamin D. Given that some clinical benefits have been demonstrated in SCD children when serum 25OHD exceeds 75 nmol/L, an effective intervention strategy aimed at normalizing vitamin D status while ensuring reasonable compliance is warranted.

HYPOTHESIS

We hypothesize that administration of a single oral bolus of 300,000 IU of vitamin D₃ to children with SCD represents a safe, acceptable and clinically feasible regimen that will result in the attainment of vitamin D sufficiency (25OHD levels >75 nmol/L) in 80% of participants and in mild improvements in some clinical outcome measures after 3 months.

RESEARCH OBJECTIVES

Primary objectives:

- To assess the feasibility of recruitment and intervention (vitamin D₃ bolus)
- To assess the acceptability of the intervention by patients and parents
- To assess the safety of the vitamin D₃ bolus (serum and urinary calcium levels, serum 25OHD)

Secondary objectives:

- To observe the mean change in total serum 25OHD from baseline to 3 months. At 3 months, a raise of the 25OHD level to 75nmol/L or more is expected.

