participation; iv) response rates to questionnaires and compliance to the interventions will be gathered throughout the trial by the research trainee.

2. *Safety*: Urine will be collected by the research nurse at baseline and 3 months and calcium/creatinine ratio measured using automated methods (Clinical Biochemistry Service, Sainte-Justine). At baseline, participants will be provided with a container to collect urine on day 7 (\pm 3days) post-bolus along with the team endocrinologist's prescription for the assessment of urine calcium and creatinine. They will be instructed to bring the urine to the nearest medical clinic for measurement. Results will be communicated to the team endocrinologist for evaluation and management. Serum calcium will be measured if deemed necessary by the endocrinologist. Code breaking will be done only if required for patient management. The proportion of children with episodes of hypercalciuria, hypercalcemia or serum 25OHD levels $>$ 250nmol/L as well as any other adverse health effects will be documented at endpoint while weekly follow-up phone calls will be made by the research trainee to inquire about adverse events.

3. *Dietary intakes and sun exposure*: The research trainee will assess calcium and vitamin D intakes at baseline and endpoint by means of a validated food frequency questionnaire¹⁵. Analysis of the FFQ will be based on values from the Canadian Nutrient File version 2010 and the US Department of Agriculture National Nutrient Database for Standard Reference as done previously¹⁶. Sun exposure will be evaluated with a non-validated questionnaire at both timepoints.

4. *Mean change of 25OHD levels*: To measure this outcome, blood will be collected at baseline and 3 months post bolus by the research nurse. Serum 25OHD will be measured in batches by tandem mass spectrometry at the Clinical Biochemistry Service of Sainte-Justine UHC.

5. *Clinical outcomes*:

Those outcomes will be either collected or measured at baseline and endpoint:

- (i) Growth: weight, height and BMI will be retrieved from medical records.
- (ii) Haematological: complete blood count, lactate dehydrogenase (as index of hemolysis), bilirubin and creatinine. These assessments are routinely performed in these children and will be extracted from medical records.
- (iii) Inflammatory: serum TNF and IL-6 will be measured by ELISA kits in [name] lab.

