Feasibility: Preliminary data showed that we already have access to a large cohort of patients (n=307) through our ongoing collaboration with two SCD expert haematologists. Infrastructure is already in place since we have previously performed data collection in more than a third of the SCD population (n=116) followed up at the clinic. Study is not invasive as those children have their blood drawn at each follow-up visits. Although a certain level of involvement is required from participants and their parents, we believe that a nutritional intervention will be perceived as more acceptable than a pharmacological treatment. For all these reasons, we anticipate few recruitment issues. Supplements (both boluses (placebo and vitamin D₃) will be provided by Euro-pharm at no cost for the study. Ethics approval will be sought and a no-objection letter will be requested from Health Canada, pending results of this review. The no-objection letter is required given that the proposed total amount of vitamin D₃ exceeds the upper intake level (UL) of vitamin D recommended for otherwise healthy children aged 4-8 years (i.e. 3,000 IU) and 9 and older (i.e. 4,000 IU).

[figure not shown]

Fig.1 Experimental design

STATISTICAL ANALYSIS

The analyses will be made using the intention-to-treat model where all subjects are included regardless of their adherence to the study protocol. Differences in outcomes between experimental groups at baseline and endpoint will be assessed using parametric Student's t test or non-parametric

Mann Whitney U test for continuous variables and Chi-square test or Fisher's exact test for categorical variables. Intragroup differences will be assessed using paired Student's t test with Bonferroni adjustment. Analyses will be performed under allocation concealment with unblinding occurring after trial completion and analysis of primary outcomes. Given the pilot nature of our study, subanalyses will be undertaken on variables that may potentially influence the response to vitamin D such as genotype, season of the year or baseline vitamin D status. However, these analyses remain exploratory.

CLINICAL SIGNIFICANCE

By implementing this pragmatic and highly acceptable intervention and achieving a compliance of 100% with the administration of the vitamin D bolus, we expect to: 1) correct vitamin D insufficiency in SCD children; 2) avoid monitoring their 25OHD levels on a regular basis; and 3) ultimately demonstrate improvements in clinical outcomes.

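### The plan names no between-arm comparison of the day-7 urine, and the baseline urinary calcium does not enter any comparison of post-bolus values between arms

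*Protocol*

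**What the plan says.** The third primary objective (Protocol, Research Objectives) is "To assess the safety of the vitamin D₃ bolus (serum and urinary calcium levels, serum 25OHD" – so urinary calcium belongs to the primary safety question.

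Methodology, Outcomes, item 2 (Safety) schedules three urine samples. Two are taken in the clinic: "Urine will be collected by the research nurse at baseline and 3 months and calcium/creatinine ratio measured using automated methods". For the third, "participants will be provided with a container to collect urine on day 7", with a window of 3 days either side; the family takes it to a nearby clinic. The one use stated for that result is "Results will be communicated to the team endocrinologist for evaluation and management". The outcome is "The proportion of children with episodes of hypercalciuria, hypercalcemia or serum 25OHD levels" above 250 nmol/L, and this, "as well as any other adverse health effects will be documented at endpoint".

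The Statistical Analysis section then says: "Differences in outcomes between experimental groups at baseline and endpoint will be assessed", by t test or Mann-Whitney for continuous variables and chi-square or Fisher for categorical ones. It adds one analysis that links a child's two values: "Intragroup differences will be assessed using paired Student's t test with Bonferroni adjustment".

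Among the exclusions (Description of the Population) are known hypercalcemia, urolithiasis, and conditions or drugs that interfere with calcium or vitamin D handling. Hypercalciuria itself is not listed.

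**The concern.** The safety question is whether the bolus raises urinary calcium above what placebo children show. Placebo is the needed reference, because both arms receive a daily vitamin D prescription and some children receive calcium. A within-arm change cannot isolate the bolus.

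Three features weaken the planned answer. The sample closest to the bolus has no named arm comparison. The baseline ratio, already collected, is not used to sharpen the comparison of later values. The hypercalciuria count does not distinguish a child who became hypercalciuric from one who already was. At stake is how precisely a small pilot can describe urinary safety for the larger trial it is meant to inform.

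**Working it through.** **1. Planned use of each urine sample**

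| Sample | Between-arm comparison named | Baseline value used in it |
|---|---|---|
| Baseline | yes | not applicable |
| Day 7 | none named | no |
| Month 3 | yes, unadjusted | no |

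The paired test uses the baseline value, but within one arm and for continuous measures. The protocol does define a change from baseline for serum 25OHD (Outcomes, item 4). It has no counterpart for urinary calcium.

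**2. Two readings of the hypercalciuria proportion**

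- *Cumulative tally reported at the end.* Day-7 episodes enter the count and are compared through it. The continuous day-7 ratio still has no comparison.
- *Status at 3 months only.* Day 7 drops out of the comparison altogether.

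The text does not choose. Under both readings, a child abnormal before the bolus who is still abnormal afterwards counts as a case.

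**3. What pre-existing cases would do**

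The protocol gives no hypercalciuria figure to reproduce, so every rate here is an assumption. Let b be the baseline prevalence, c and t the new-case risks on placebo and bolus, and suppose every baseline-abnormal child counts as a case.

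Observed risk = b + (1 − b) × new-case risk, so observed difference = (1 − b)(t − c).

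With c = 5%, t = 25%:

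| b | Placebo | Bolus | Difference (points) | Risk ratio |
|---|---|---|---|---|
| 0% | 5.0% | 25.0% | 20 | 5.00 |
| 5% | 9.8% | 28.7% | 19 | 2.95 |
| 10% | 14.5% | 32.5% | 18 | 2.24 |
| 20% | 24.0% | 40.0% | 16 | 1.67 |
| 30% | 33.5% | 47.5% | 14 | 1.42 |

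Both arms move together, so contrast is lost but neither arm is favoured. By chance alone, with b = 10% and 36 per arm, the difference in pre-existing cases has SD √(2 × 0.1 × 0.9/36) = 7.1 points, and a gap of 3 or more children has probability 0.32.

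**4. Would counting only new cases recover power?**

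Fisher's exact test, two-sided 5%, by full enumeration. The Sample size section plans 36 recruited and 30 needed per arm. New-case analyses use (1 − b) of these, rounded. Cells show power counting all cases / new cases only:

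| New-case risks, n per arm | b = 5% | b = 10% | b = 20% |
|---|---|---|---|
| 25% v 3%, 36 | 55 / 66% | 42 / 61% | 28 / 53% |
| 25% v 3%, 30 | 43 / 50% | 34 / 47% | 22 / 52% |
| 25% v 5%, 30 | 34 / 39% | 27 / 36% | 18 / 40% |
| 10% v 3%, 36 | 6.5 / 4.9% | 6.3 / 4.1% | 5.0 / 2.9% |

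Fisher power is saw-toothed at these sizes (hence 47% rising to 52% in the second row), so the gaps are approximate. With a large effect the new-case count helps. With 10% v 3% it gains nothing.

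**5. What the baseline covariate would do**

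If the baseline and later ratios correlate at r within arms, adjustment multiplies the variance of the arm difference by about 1 − r², against an unadjusted comparison of follow-up values. The documents give no r. Over an assumed range:

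- r = 0.3: 1 − 0.09 = 0.91
- r = 0.5: 1 − 0.25 = 0.75
- r = 0.7: 1 − 0.49 = 0.51

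At r = 0 the cost is about one degree of freedom. This gain does not depend on any child being hypercalciuric at baseline.

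**The case against.** The best defence is that the proportion, documented at the end of follow-up, is naturally a cumulative tally, so a day-7 episode is already compared. A reader might infer that the day-7 sample is discarded. The text does not support that as fact: sending a result to the endocrinologist does not stop it being counted. What stands is narrower, namely that no day-7 comparison is named and the ratio itself is not compared at that time.

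A reader might also infer that pre-existing cases bias the safety result. They do not. Allocation is random, so such cases fall evenly on average and the loss is one of precision. The exclusion of conditions and drugs affecting calcium metabolism may remove some of them, and their number is unknown.

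A third inference is that outside clinics' limits decide who is a case. The protocol does not say so. All day-7 results go to one endocrinologist, and blinding means laboratory differences should affect both arms alike.

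It is fair, too, that the cut-off and the detailed case definition are usual content for an analysis plan, that unadjusted tests are valid in a randomised trial, and that the study is a pilot not powered on safety. Finally, confining the main denominator to children normal at baseline would sit badly with the stated intention-to-treat principle and would take worsening in the others out of view. These objections limit the point. They do not answer it, because the protocol itself fixes unadjusted tests at two times.

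**Conclusion.** The point holds as an inexpensive improvement to the analysis of a primary safety measure, not as an error that invalidates it. What rests on the text alone is that no between-arm comparison is named at day 7, that no between-arm comparison of post-bolus urinary calcium uses the baseline value, and that the proportion does not separate new from pre-existing cases.

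The size of the dilution cannot be estimated from the documents. It is zero if no child is hypercalciuric at baseline. Under the assumed 25% v 5% it takes 1 to 6 points off a 20-point difference for prevalences of 5% to 30%. Any power gain from counting only new cases depends on a large effect, so the calculations do not support making that the main analysis. The covariate adjustment is the sounder gain, with its size set by an unknown correlation.

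**What to change.** In Statistical Analysis, add a between-arm comparison of the urinary calcium/creatinine ratio at day 7 and at month 3, each with the baseline ratio as covariate, in common units and transformed if skewed.

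In Outcomes, item 2 (Safety), state that an episode of hypercalciuria is a post-bolus value, at day 7 or month 3, judged by one analysis definition fixed before unblinding. Report the proportion among all children, with an exact interval for the difference between arms. As supplementary displays, show new cases among children normal at baseline, and show children abnormal at baseline separately.

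All three samples are already scheduled, so nothing new is collected. The cost is a few sentences of wording and a little extra analysis.

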- To observe the effects of the vitamin D₃ bolus intervention in improving growth (height, weight and BMI), haematological (fetal hemoglobin), inflammatory (TNF and IL-6), bone health (PTH, biochemical markers of bone formation and resorption, musculoskeletal pain) and quality of life.

DESCRIPTION OF THE POPULATION

The children who will participate in this study are the ones who are followed at the Sainte-Justine UHC SCD clinic. Inclusion criteria: Children aged 5 to 17 years regardless of SCD genotypes (e.g. HbSS, HbSC, HbS/β-thalassemia, others). We purposely choose to include all genotypes since our preliminary data showed that they did not differ much in terms of vitamin D status and should therefore all benefit from optimizing vitamin D nutrition. Exclusion criteria include: conditions or

use of medications known to interfere with calcium or vitamin D absorption or metabolism, known hypercalcemia, conditions characterized by a hypersensitivity to vitamin D (e.g. granulomatous disorders), patients clinically diagnosed with rickets or other conditions requiring vitamin D therapy, history or presence of urolithiasis, anticipated difficult follow up, patients already enrolled in other investigational studies, recent hospitalization for severe pain crisis or acute sickle complication in the past 2 weeks and unresolved pain issues.

PARTICIPANTS APPROACH

Children attending the Sainte-Justine UHC SCD clinic will be screened for enrollment by a research trainee. Eligible children and parents will be approached at their next follow up appointment at the clinic by the collaborating haematologists. The children and parents interested to participate in the study will then meet the research trainee for a more in depth description of the study and to answer any questions they could have. The consent form will be signed in the presence of the research trainee the same day or during the patient's next appointment at the clinic.

METHODOLOGY

Design: We propose to carry out a pilot double-blind RCT in children aged 5-17 years followed up at the SCD clinic of Sainte-Justine UHC.

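### Growth in children aged 5 to 17 is compared between arms by an unadjusted endpoint test that ignores baseline, so age swamps any 3-month effect on height

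*Protocol*

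**What the plan says.** The secondary objectives (Research Objectives) include observing the effect of the bolus in "improving growth (height, weight and BMI"). The population is "Children aged 5 to 17 years regardless of SCD genotypes".

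Under Outcomes, item 5 (i), "weight, height and BMI will be retrieved from medical records". On timing, the same item says: "Those outcomes will be either collected or measured at baseline and endpoint".

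The Statistical Analysis section gives one rule for all continuous outcomes: "Differences in outcomes between experimental groups at baseline and endpoint will be assessed using parametric Student's t test or non-parametric" Mann-Whitney. For change within an arm, "Intragroup differences will be assessed using paired Student's t test with Bonferroni adjustment". The variables named for exploratory subanalysis are "such as genotype, season of the year or baseline vitamin D status"; age and sex are not among them. Randomisation is described as permuted blocks, with no stratification by age or sex mentioned.

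For 25OHD the Protocol names mean change as the outcome. For growth it names no change, velocity, percentile or z-score.

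**The concern.** Between 5 and 17 years a child's height depends mostly on age. A two-sample test on height at 3 months therefore compares two groups whose spread is nearly all age, in search of an effect that cannot reasonably exceed a fraction of 3 months' growth. The baseline height of the same child would remove almost all of that spread, but the stated between-group test does not use it.

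Two things follow. A real effect would be missed almost as often as if the test were not done. And if one arm happened to be older, the endpoint difference would look like a growth effect several times larger than anything 3 months could produce. The paired tests do use baseline, but only within an arm. Growing children gain height with or without vitamin D, so a significant paired result does not separate treatment from normal growth.

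**Working it through.** The Protocol gives no power figure, SD or expected effect for growth. Its sample size is derived for 25OHD sufficiency only, so there is no stated growth figure to reproduce.

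**Inputs from the Protocol**
- Age 5 to 17 years.
- 36 per group with 20% attrition: 36 × 0.8 = 28.8, taken as 29 per arm.
- Follow-up of 3 months.
- Two-sided α = 0.05.

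**Assumptions (not in the Protocol)**
- Age uniform over 5-17.
- Mean growth 4-6 cm/year.
- Within-age height SD 6.5 cm.
- Residual SD of the 3-month height z-score given baseline, 0.05-0.20.
- Illustrative effect 0.1 z, which is 0.1 × 6.5 = 0.65 cm.

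**Step 1. Spread of raw height.**
SD of age = 12/√12 = 3.46 years. Total SD = √[(3.46 × slope)² + 6.5²].
- 4 cm/year: √(13.86² + 6.5²) = 15.3 cm; age share of variance 82%.
- 6 cm/year: √(20.78² + 6.5²) = 21.8 cm; age share 91%.

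**Step 2. Difference detectable with 80% power.**
2.80 × SD × √(2/29), where √(2/29) = 0.263.
- 2.80 × 15.3 × 0.263 = 11.3 cm.
- 2.80 × 21.8 × 0.263 = 16.0 cm.

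Total growth in 3 months is 4/4 to 6/4, or 1.0-1.5 cm.

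**Step 3. Power of the stated test.**
For a 0.65 cm effect the noncentral t gives 5.1-5.3%, essentially the false-positive rate.

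**Step 4. Chance age imbalance.**
Standard error of the between-arm difference in mean age = 3.46 × 0.263 = 0.91 years. At 5 cm/year that is about 4.5 cm of height (3.6-5.5 cm over 4-6 cm/year), at least twice all the growth that occurs in the trial.

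**Step 5. Which change matters?**

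| Analysis of height, 29 per arm | SD used | Detectable, 80% power | Power for 0.1 z (0.65 cm) |
|---|---|---|---|
| Raw endpoint | 15.3-21.8 cm | 11-16 cm | about 5% |
| z-score endpoint, no baseline | 1 z | 0.74 z (4.8 cm) | 6.6% |
| z-score adjusted for baseline | 0.05 z | 0.04 z (0.2 cm) | about 100% |
| Same | 0.10 z | 0.07 z (0.5 cm) | 96% |
| Same | 0.12 z | 0.09 z (0.6 cm) | 88% |
| Same | 0.20 z | 0.15 z (1.0 cm) | 46% |

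Standardising for age without baseline barely moves the power; using baseline does. A check on the raw scale agrees. With 30 per arm and an assumed SD of 0.6-1.5 cm for 3-month height change, the detectable difference in change is 0.4-1.1 cm.

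Once baseline is used, z-scores add a smaller gain. In a simulation with an illustrative height curve and measurement error of 0.2-0.5 cm, the standard error from z-score ANCOVA was 7-22% smaller than from raw ANCOVA.

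**The case against.** The strongest objection is that the sentence on growth describes only where the data come from. Nowhere does the Protocol say that raw centimetres or kilograms will be analysed in preference to z-scores. Age and sex are collected, and deriving a z-score is a step commonly left to a statistical analysis plan. This stands. A reader might infer that the Protocol has chosen raw values over z-scores, but the text is silent on that. What it does state is the between-group test, and that test makes no use of baseline whatever the scale.

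A reader might also infer that converting to z-scores would by itself repair the comparison. It would not: power stays at about 6-7%. Nor does adding baseline guarantee high power. At a residual SD of 0.20 z it is about 46% for a 0.1 z effect.

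Third, the stakes are small. The aim is to observe effects in a pilot whose primary objectives are feasibility, acceptability and safety. The Protocol itself concedes that 3 months is short for clinical improvement, and no decision hangs on growth. This stands too. It would be too strong to say that the growth data cannot inform a larger trial, because both measurements are held and a better analysis can be run on them without new data.

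**Conclusion.** The point holds as a minor one. The stated between-group rule, applied to height in children aged 5 to 17, has about 5% power for a plausible 3-month effect. Its detectable difference of 11-16 cm is roughly ten times the growth available (11.3/1.0 to 16.0/1.5), and a chance age imbalance would dominate the estimate. The cause is chiefly that baseline is ignored. The lack of stated age and sex standardisation is secondary.

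The sizes rest on the assumed age distribution, growth rate, within-age SD and residual SD, none of which the Protocol gives. The conclusion does not depend on where in those ranges the truth lies. Only height has been quantified. Weight and BMI fall under the same rule, but no figure is offered for them.

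**What to change.** In the Statistical Analysis section, replace the endpoint test for growth with a between-arm comparison of the 3-month value adjusted for the baseline value (ANCOVA). Preferably, express height, weight and BMI as age- and sex-specific z-scores at both visits, from one named reference and at exact age on the day of measurement. This gives a scale that means the same at 5 and at 17. Report raw values descriptively, and do not read the paired within-arm tests as evidence of a treatment effect.

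The cost is programming only: age, sex, height and weight at both visits are already being collected. Sample size, visits and procedures do not change.
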